2 STUDY OBJECTIVES

The primary objective of this study is to evaluate the effect of NTZ administered orally 600 mg b.i.d. for 5 days in reducing the duration of symptoms of influenza compared to that of a placebo during 21 days of follow up based upon the FLU-PRO[®] patient-reported outcome instrument.

A key secondary efficacy objective is to evaluate the effect of NTZ compared to placebo on time to return to ability to perform all normal activities.

Another secondary efficacy objective is to evaluate the effect of NTZ compared to placebo on the proportion of subjects experiencing one or more complications of influenza including pneumonia, otitis media, bronchitis, sinusitis, worsening of pre-existing health conditions, systemic antibiotic use for infections secondary to influenza infection, hospitalization due to complications of influenza, and death.

Exploratory efficacy objectives include evaluating the effect of treatment with NTZ on the time to response for each FLU-PRO symptom, time to response for each FLU-PRO domain, time to resolution of febrile illness, time to return to usual health, and changes in viral titers from baseline to each of days 2, 3 and 7.

Other important objectives include evaluation of the safety of NTZ by analysis of adverse events and evaluation of the effect of nitazoxanide on influenza antibody response and evaluation of relationships between pharmacokinetics and clinical or virologic responses.

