8.2 Efficacy Variables

Primary Efficacy Parameter: Time from first dose until Symptom Response

Secondary Efficacy Parameters:

- i. Time from first dose until subjects are able to perform 100% of normal activities (i.e., a score of 10 on the scale of 0-10)
- ii. Proportions of subjects experiencing one or more complications of influenza including pneumonia, otitis media, bronchitis, sinusitis, worsening of pre-existing health conditions, systemic antibiotic use for infections secondary to influenza infection, hospitalization due to influenza or complications of influenza and death
- iii. Time to Symptom Response excluding the FLU-PRO Gastrointestinal and Eye domains

Exploratory Efficacy Parameters:

- i. Time to Individual Symptom Response
- ii. Time to FLU-PRO Domain Response
- iii. Time to Resolution of Acute Febrile Illness
- iv. Time to Return to Usual Health

- v. Change in influenza virus titer (TCID₅₀) from baseline to day 2 and from baseline to day 3
- vi. Proportions of subjects with virus detected in nasopharyngeal swabs collected at each of days 2, 3 and 7 by culture and by RT-PCR

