8.4.1 Efficacy Analyses

Efficacy analyses will be based on a population consisting of all subjects that received at least one dose of study drug and had laboratory-documented influenza infection (infected intent-to-treat or ITTI population). Laboratory-documented influenza infection is defined by identification of influenza virus in nasopharyngeal secretions by RT-PCR or viral culture at baseline, day 2 or day 3.

There will be one primary efficacy analysis:

- Time to Symptom Response for the NTZ treatment group will be compared to that of the placebo treatment group using a stratified Gehan-Wilcoxon test ($\alpha = 0.05$) stratified by (1) time since symptom onset for each subject at enrollment (≥ 24 hours, $>24 - 36$ hours, >36 hours) and (2) whether the subject received seasonal influenza vaccination after August 1, 2018. Subjects without a Symptom Response being recorded will be treated as censored as of their last diary without a documented Symptom Response.

If the primary analysis is significant at the 0.05 level, a key secondary efficacy analysis will be formally evaluated at the 0.05 level as follows:

- Time to Ability to Perform All Normal Activities for the two treatment groups will be compared using a stratified Gehan-Wilcoxon test ($\alpha = 0.05$) stratified by (1) time since symptom onset for each subject at enrollment (≥ 24 hours, $>24 - 36$ hours, >36 hours) and (2) whether the subject received seasonal influenza vaccination after August 1, 2018. Subjects without an Ability to Perform All Normal Activities response being recorded will be treated as censored as of their last diary without a documented Ability to Perform All Normal Activities response.

If both the primary analysis and the key secondary efficacy analysis are significant at the 0.05 level, another secondary efficacy analysis will be formally evaluated at the 0.05 level as follows:

- Proportions of subjects experiencing one or more complications of influenza including pneumonia, otitis media, bronchitis, sinusitis, worsening of pre-existing health conditions, systemic antibiotic use for infections secondary to influenza infection, hospitalization due to influenza or complications of influenza and death will be compared between the treatment groups using a Fisher's exact test ($\alpha = 0.05$).

A third secondary analysis will be performed as follows:

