10 ADVERSE EVENTS

The term “adverse event” is defined for purposes of this study as any unwanted physical, psychological or behavioral change experienced by a subject during the course of the study and after taking the first dose of study medication regardless of its severity or relation to the study. Adverse events may include symptoms, signs, unexpected worsening of pre-existing conditions, clinically significant changes in laboratory values, diseases and syndromes, and significant and unexpected failures of pharmacological action of other medications. Symptoms of influenza (i.e., those captured in the FLU-PRO Questionnaire) and complications of influenza (e.g., pneumonia, otitis media, bronchitis, sinusitis) shall not be reported as adverse events unless

there is a causal relationship between the study medication and the event. These symptoms and complications will be analyzed separately from adverse events as they are study endpoints.

Bacterial pneumonia, acute bacterial otitis media and acute bacterial sinusitis will be reported as complications of influenza only if the following criteria are satisfied:

Bacterial pneumonia:

1. At least two of the following symptoms: difficulty breathing, cough, production of purulent sputum, chest pain
2. At least two of the following vital sign abnormalities: fever, hypotension, tachycardia, tachypnea
3. At least one of the following findings: hypoxemia, clinical evidence of pulmonary consolidation, elevated white blood cell count or leukopenia
4. Chest radiograph findings of new infiltrates in a lobar or multilobar distribution.
5. Microbiologic criteria: appropriate sputum specimen with fewer than 10 squamous epithelial cells and more than 25 polymorphonuclear cells per low power field

Acute bacterial otitis media:

1. Symptoms of ear pain or earache, ear fullness or decreased hearing
2. One or more of the following otoscopic findings performed by a clinician experienced in otoscopy:
 - Bulging or fullness of the tympanic membrane (convexity of the plane of the eardrum), with loss of anatomic landmarks on visualization,
 - Opacification of the tympanic membrane regardless of color,
 - Erythema of the tympanic membrane, or

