10.4.2 Proportion of Subjects Experiencing Complications of Influenza

Variables Used for the Analysis

The analysis will require the following variables:

Variable	Source	Format/Notes
Complications of influenza	CRF	Investigators will designate an adverse event as a complication of influenza if the event meets protocol-specified criteria

Analysis

Proportions of subjects experiencing one or more complications of influenza will be compared between the treatment groups using a Fisher’s exact test.

Analysis Population(s):	Confirmed Influenza
Derived Variables:	None

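### SAP 10.4.2 builds the complications endpoint from adverse events, which Protocol 10 says complications are not unless drug-caused, and it gives no derivation for the antibiotic component

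*SAP*

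**What the plan says.** SAP 10.4.2 has one input row, named for complications of influenza, with the CRF as its source. The only rule is "Investigators will designate an adverse event as a complication of influenza if the event meets protocol-specified criteria". The entry for derived variables is none, and the test is Fisher's exact test in the Confirmed Influenza population.

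Protocol 10 sets the reporting rule. Influenza symptoms "and complications of influenza (e.g., pneumonia, otitis media, bronchitis, sinusitis) shall not be reported as adverse events unless" study medication caused the event. It gives the reason: "These symptoms and complications will be analyzed separately from adverse events as they are study endpoints". It then adds a threshold for three diagnoses: "Bacterial pneumonia, acute bacterial otitis media and acute bacterial sinusitis will be reported as complications of influenza only if the following criteria are satisfied".

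The composite is defined in Protocol 8.2 and repeated in 8.4.1. It covers pneumonia, otitis media, bronchitis, sinusitis and worsening of pre-existing conditions, and ends with "systemic antibiotic use for infections secondary to influenza infection, hospitalization due to influenza or complications of influenza and death".

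SAP 10.4 tests this endpoint formally at 0.05 only if the primary and the normal-activities analyses are both significant.

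**The concern.** An event that sites are told not to report as an adverse event cannot later be picked out of the adverse events. Applied as written, the two rules together would let a pneumonia, otitis media, bronchitis or sinusitis into the efficacy count only when it was attributed to study drug. That is close to the opposite of what an efficacy endpoint should count.

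The antibiotic component has a different problem. Antibiotic use is a treatment, so it does not arise from designating events at all, and SAP 10.4.2 offers no other route.

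At stake is whether the third formal test analyses the protocol's composite, and whether two programmers working from this text would get the same count. If the source is settled at programming, the endpoint has not been fully pre-specified.

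**Working it through.** The documents give no rate, power or expected count for this endpoint, so there is no figure to reproduce. The check is a comparison of text.

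**1. The source rule against the reporting rule.** SAP 10.4.2 starts from adverse events. Protocol 10 removes complications from adverse events, with drug causality as the only exception. Protocol 3 also has sites presume during the study that any complication is influenza-related, so the exception should be uncommon. The two rules cannot both be followed and still yield the composite of Protocol 8.2.

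**2. Could a separate complications record supply the data?** Several places point that way:
- Protocol 5.4 and 5.5 put the complication screening of Days 2 to 5 into the case report forms.
- Protocol 3 names complications beside adverse events as items reported at Days 7 and 22.
- SAP 10.7 has a complications listing of its own, without the seriousness and drug-relationship columns of the adverse event listing in SAP 11.2.

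Others point away:
- SAP 10.4.2 names no such form or field.
- The procedure lists for Day 7 (Protocol 5.6) and Day 22 (Protocol 5.7) include adverse event review but no complications item.
- The schedule in Protocol Appendix I marks complication screening only in the columns for Days 2 to 5.

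The record is plausible but not established, and after Day 5 only the general statement in Protocol 3 supports it.

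**3. The antibiotic component if that record exists.** The complications listing in SAP 10.7 holds event terms, dates, severity, outcome and whether treatment was required. It has no medication name, indication or route. Those fields are in the concomitant medication listing of SAP 9.2, and Protocol 5.10 has the diary record the reason for each medication. Nothing links either to this endpoint. By contrast, SAP 10.4.1, the section just before, names a medication listing as an input.

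**4. A case where the count changes.** Protocol 10 requires radiographic findings, among other criteria, before bacterial sinusitis is reported as a complication. Take a subject given a systemic antibiotic for a secondary sinusitis that was never imaged. The diagnosis fails the criteria, but the subject meets the antibiotic component of Protocol 8.2. SAP 10.4.2 has no route by which that subject is counted.

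**5. The criteria invoked.** Protocol 10 gives criteria for bacterial pneumonia, otitis media and sinusitis only. For bronchitis, worsening of pre-existing conditions, antibiotic use and hospitalization, the SAP's appeal to criteria in the protocol has nothing to refer to.

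**6. Hospitalization wording.** Protocol 2, SAP 3 and SAP 7.1 use the narrow form, "hospitalization due to complications of influenza, and death". The synopsis and Protocol 8.2 and 8.4.1 also include hospitalization due to influenza itself.

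**Illustration under assumed rates.** Inputs: 300 per arm (SAP 7.3), two-sided Fisher test at 0.05, and the same capture fraction *f* in both arms, so that the observed rates are *f* × p(placebo) and *f* × p(NTZ). The rates and *f* are assumptions.

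| Assumed true rates | f = 1 | f = 0.75 | f = 0.50 | f = 0.25 |
|---|---|---|---|---|
| 10% vs 5% | 59.3% | 44.6% | 29.6% | 12.2% |
| 5% vs 2.5% | 29.6% | 20.9% | 12.2% | 3.9% |

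At 10% vs 5% with *f* = 0.50, the expected counts fall from 300 × 0.10 = 30 and 300 × 0.05 = 15 to 15 and 7.5. This shows the direction of the effect, not its size in this trial.

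**The case against.** The strongest defence is that SAP 10.4.2 describes a sorting step. The investigator sees an untoward event, judges it against the protocol, and records it as a complication instead of an adverse event. The CRF source, the separate listing in SAP 10.7 and the separate mention in Protocol 3 all fit that reading, and the CRF itself cannot be checked. This stands as a plausible account of what was intended. It does not remove the conflict in the written rule, and it leaves the antibiotic component underived.

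On antibiotics, it can be said that the CRF is also the source of concomitant medication use in SAP 10.6.2, and that an infection treated with an antibiotic can itself be recorded as an event. That is fair: the data are probably available, and what is missing is the link and the derivation. The sinusitis case shows that recording the infection is not always enough.

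A reader might go further and count how many of the eight components have no route under the literal rule. The documents do not support a firm count. Protocol 10 gives its diagnoses only as examples. It also says "Adverse events may include symptoms, signs, unexpected worsening of pre-existing conditions", while Protocol 5.4 lists worsening of pre-existing conditions among influenza-related complications. Hospitalization and death reach the serious adverse event record, but Protocol 10.1 defines that record in terms of adverse experiences. Any split would be the reader's own classification.

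The hospitalization difference is confined to objectives text. The variable and analysis definitions agree with each other, so it is a matter of tidying.

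Materiality is limited. The test is formal only after two earlier successes, and Protocol 3 does not expect enough complications to show a difference. Investigators are masked, and nothing in the documents shows bias between arms.

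**Conclusion.** The concern holds for the written rule. SAP 10.4.2 takes its input from a pool that Protocol 10 empties of the events it needs, and following it literally gives a variable other than the one in Protocol 8.4.1. If an unnamed CRF complications record is assumed, most of the conflict becomes a wording fault. The antibiotic component still has no stated link to medication data.

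It would be wrong to infer that complications data are not collected, or that the result would favour one arm. The documents suggest collection on Days 2 to 5 and, more loosely, at Days 7 and 22, and they give no basis for a direction of bias.

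The number of subjects affected cannot be determined. The primary and key secondary analyses are untouched. This should be corrected before unblinding; it does not threaten the trial's main conclusion.

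**What to change.** Before unblinding, replace the adverse event designation in SAP 10.4.2 with a composite derived regardless of adverse event status or causality. A subject counts if any of these is present:

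1. A complication recorded by the investigator in the CRF, with the form or field named, and with the Protocol 10 criteria applied to the bacterial diagnoses as the protocol states them.
2. Systemic antibiotic use for an infection secondary to influenza, taken from concomitant medication records by indication and route, and kept as its own component.
3. Hospitalization due to influenza or its complications, or death, from CRF and serious adverse event records.

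State that the hospitalization wording of Protocol 8.2 and 8.4.1 ("hospitalization due to influenza or complications of influenza and death will be compared between the treatment groups") is the one analysed, and reconcile Protocol 2, SAP 3 and SAP 7.1 with it. The documents do not say whether a bacterial diagnosis that fails its criteria may still count as the plain diagnosis, so the SAP revision should not assume an answer without the sponsor's decision.

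The cost is a short derivation paragraph and some programming. Medication reason, indication and route (Protocol 5.10, SAP 9.2), screening results (Protocol 5.4 and 5.5) and serious event reports (Protocol 10.2) are already planned. SAP 6 allows revision before database lock. The item to confirm against the CRF is where complications after Day 5 are recorded.

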10.4.3 Time to Modified Symptom Response Excluding FLU-PRO Gastrointestinal and Eye Domains

This analysis will repeat the methodology for deriving and analyzing the Time to Symptom Response, but will exclude from consideration those FLU-PRO items in the Eye and Gastrointestinal domains. Excluded items will be: teary or watery eyes, sore or painful eyes, eyes sensitive to light, felt nauseous (feeling like you wanted to throw-up), stomach ache, vomit (frequency), and diarrhea (frequency).

Definitions:

Modified Symptom Response The set of criteria to be defined based upon a blinded review of symptom scores from only the Nose, Throat, Chest/Respiratory, and Body/Systemic domains (pooled for all influenza-infected subjects without regard to treatment group assignment) that correlate to the time at which subjects report that they return to usual health (a daily global assessment question). Methodology to be used for the derivation of the Modified Symptom Response definition is described in detail below. Symptom scores must be maintained at the defined level for at least 2 daily diary periods without any symptom relief medication during or between those 2 daily diary periods.

Time of Modified Symptom Response The start of the first daily diary period in which Modified Symptom Response is achieved and is maintained for at least two daily diary periods without any symptom relief medication during or between those two daily diary periods.

Time to Modified Symptom Response Time (hours) from the first dose of study medication to the Time of Modified Symptom Response.

Variables Used for the Analysis

The analysis will require the following variables:

Variable	Source	Format/Notes
Date and time of first medication intake	CRF	
Date and time of completion for each symptom assessment record	Subject diary	
Symptom score assessment for each symptom for each diary record except those belonging to the Eye and Gastrointestinal domains	Subject diary	
The ordinal symptom severity, intensity or frequency score assessment for each of the 25 symptoms will be coded to numerical values 0-4. The numerical values represent ordinal responses and therefore cannot be summed, averaged, or treated as continuous data.
 
It will not be possible for any individual symptom assessment to be missing within a diary record, therefore no individual item imputation will be required.
 
In the event that the diary was not completed at a specified time point (e.g., Day 2), the missing data will not be imputed.

Date and time of symptom relief medication intake	Sponsor-provided listing	The list of symptom relief medications will be selected from the listing of all concomitant medications prior to unblinding.

Derivation of the Modified Symptom Response Definition

Derivation of the Modified Symptom Response definition will be accomplished using the procedure in section 10.2.1 applied to only the 25 FLU-PRO items in the Nose, Throat, Chest/Respiratory, and Body/Systemic Domains.

Analysis

The efficacy parameter, time to Modified Symptom Response, will be derived as follows:

Event: Time of Modified Symptom Response – time of the first dose

Censored: Time of last symptom assessment – time of the first dose

If Modified Symptom Response is achieved at the time of the first symptom assessment diary record, the subject will be excluded from the analysis.

If the Modified Symptom Response is not achieved prior to a subject’s last diary available assessment, but the criteria are met at the last available diary assessment with no evidence of symptom relief medication intake during that diary period, Time of Modified Symptom Response will be considered to have occurred at the start of the last daily diary period.

Time to Modified Symptom Response for the NTZ treatment group will be compared to that of the placebo treatment group using a Gehan-Wilcoxon test stratified for (1) time from onset of illness to time of first dose of study medication (0-24, >24-≤36, or >36 hours from onset), and (2) vaccination status (Y/N). The comparison will be graphically depicted using Kaplan-Meier curves.

Analysis Population(s):	Confirmed Influenza
Derived Variables:	Event: Time of Modified Symptom Response – time of the first dose Censored: Time of last symptom assessment – time of the first dose

10.5 Exploratory Efficacy Analyses

10.5.1 Time to Individual Symptom Response

Definitions:

Individual Symptom Response For each individual symptom (n=32), a score of ≤ the maximum response value specified by the Symptom Response definition maintained for at least two consecutive daily diary periods without symptom relief medication during or between those daily diary periods.

Time of Individual Symptom Response

The start of the first daily diary period in which Individual Symptom Response is achieved and is maintained for at least two daily diary periods without any symptom relief medication during or between those two daily diary periods.

Time to Individual Symptom

Response Time (hours) from the first dose of study medication to the Time of Individual Symptom Response.

Variables Used for the Analysis

The analysis will require the following variables:

Variable	Source	Format/Notes
Date and time of first medication intake	CRF	
Date and time of completion for each symptom assessment record	Subject diary	
Symptom score assessment for each symptom for each diary record	Subject diary	The ordinal symptom score assessment for each of the 32 symptoms will be coded to numerical values 0-4. In the event that the diary was not completed at a specified time point (e.g., Day 2), the missing data will not be imputed.
Date and time of symptom relief medication intake	Sponsor-provided listing	The list of symptom relief medications will be selected from the listing of all concomitant medications prior to unblinding. Subjects will report the reason for taking each symptom relief medication, and this data will be used to assign concomitant medications to relevant flu symptoms reported in the FLU-PRO questionnaire.

Analysis

The efficacy parameter, time to Individual Symptom Response, will be derived as follows:

Event: Time of Individual Symptom Response – time of the first dose

Censored: Time of last symptom assessment – time of the first dose

If Individual Symptom Response is achieved at the time of the first symptom assessment diary record, the subject will be excluded from the analysis.

If the Individual Symptom Response is not achieved prior to a subject’s last available diary assessment, but the criteria are met at the last available diary assessment with no evidence of symptom relief medication intake during that diary period, Time of Individual Symptom Response will be considered to have occurred at the start of the last daily diary period.

Time to Individual Symptom Response for the NTZ treatment group will be compared to that of the placebo treatment group using a Gehan-Wilcoxon test stratified for (1) time from onset of illness to time of first dose of study medication (0-24, >24-≤36, or >36 hours from onset), and (2) vaccination status (Y/N). The comparison will be graphically depicted using Kaplan-Meier curves.

Analysis Population(s):	Confirmed Influenza
-------------------------	---------------------

Derived Variables:	Event:	Time of Individual Symptom Response – time of the first dose
	Censored:	Time of last symptom assessment – time of the first dose

